- TMZ treatment should also be coordinated to start on the first day of RT, but starting no more than 7 days after start of RT is acceptable and will not be recorded as a treatment delay. TMZ may start within 24 hours before RT, per investigator discretion.

Sequence of Starting Trimodal Therapy

^A TTField therapy can start as soon as the same day as the day 1 clinic visit, no more than 7 days after the day 1 visit (Day 1 to Day 8), and up to 14 days before RT/TMZ initiation.

^B TTField therapy must be initiated prior to RT simulation and mask preparation. Preferably, patients would have the TTF initiated for a few days prior to radiation therapy to adjust for user errors and patient issues.

^C RT should be initiated no more than 14 days after the day 1 visit (by Day 15).

^D Subjects will receive radiation therapy within 4-6 weeks of their surgical resection or 2-4 weeks of their biopsy for the purpose of ensuring proper wound-healing.

^E TMZ treatment should also be coordinated to start on the first day of RT, but starting no more than 7 days after start of RT is acceptable and will not be recorded as a treatment delay (by Day 22). TMZ may start within 24 hours before RT, per investigator discretion.

During this phase, study procedures should be completed +/- 7 days from the Day specified unless otherwise noted.

During this phase, patients will undergo weekly skin checks by radiation oncology or neuro-oncology. Transducer arrays must be off the skin in order to perform a careful examination of the skin for toxicity. The patient and physician needs to time the changing of transducer arrays such that the arrays are not worn during weekly visits. The same practice applies to skin checks after the trimodal therapy phase and during adjuvant treatment per the standard of care.

Trimodal therapy, Day 1 (21-42 days from surgery or 14-28 days from stereotactic biopsy)

The following procedures are to be completed on Day 1 prior to TTField initiation:

- Vital signs: weight, temperature, pulse, respiration rate, and resting blood pressure.
- Physical examination including neurologic exam, head and neck exam, and scalp exam to evaluate surgical healing and contraindications to radiation and TTField therapy.
- Adverse event assessment
- Concomitant medication review
- KPS (performance) assessment
- Complete blood count (CBC) with differential and platelet count (if completed for screening within 14 days of Day 1, does not need to be repeated)

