Day 36 (± 7 days)

- Skin examination by investigator or subinvestigator in Radiation Oncology or Neuro-Oncology (document attribution, grade of toxicity, and if there is apparent correlation with the ceramic disc or adhesive gel on the transducer arrays). Treatment of mild skin toxicity as appropriate. If there are concerns of worsening skin toxicity, referral to dermatologist for specialist evaluation (transducer arrays will need to be removed/replaced for exam).
- Complete blood count (CBC) with differential and platelet count
- Adverse event assessment
- Concomitant medication review
- Continuation of TTField Therapy
- Continuation of RT
- Continuation of TMZ therapy

Day 43 (± 7 days) Final week of Trimodal therapy

- Skin examination by investigator or subinvestigator in Radiation Oncology or Neuro-Oncology (document attribution, grade of toxicity, and if there is apparent correlation with the ceramic disc or adhesive gel on the transducer arrays). Treatment of mild skin toxicity as appropriate. If there are concerns of worsening skin toxicity, referral to

dermatologist for specialist evaluation (transducer arrays will need to be removed/replaced for exam).

- Neurological examination by investigator or subinvestigator in Radiation oncology or Neuro-oncology.
- Complete blood count (CBC) with differential and platelet count
- Adverse event assessment
- Concomitant medication review
- Continuation of TTField Therapy
- Continuation of RT until Day 49 + 7 days, as clinically appropriate
- Continuation of TMZ therapy until Day 49 + 7 days, as clinically appropriate

Day 64 (± 7 days) Post initial chemoradiation continued DLT window

This is marked by continued TTField therapy alone for 4 weeks with the following procedures for continued monitoring of DLTs and TRAEs. One visit to be conducted in the middle of the 4 weeks with the following procedures.

- Vital signs: weight, temperature, pulse, respiration rate, and resting blood pressure.
- Skin examination by investigator or subinvestigator in Neuro-Oncology (document attribution, grade of toxicity, and if there is apparent correlation with the ceramic disc or adhesive gel on the transducer arrays). Treatment of mild skin toxicity as appropriate. If there are concerns of worsening skin toxicity, referral to dermatologist for specialist evaluation (transducer arrays will need to be removed/replaced for exam).
- Physical examination including neurologic exam, skin and scalp assessment.

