b) Concomitant chemoradiation: The use of radiation therapy and temozolomide chemotherapy for patients with newly diagnosed glioblastoma is considered standard of care. Furthermore, TTField therapy with Optune™ is also approved for post-radiation adjuvant treatment of newly diagnosed glioblastoma (see preclinical data). The use of these treatment modalities will follow established parameters and guidelines and will be briefly reviewed in this section. However, trimodal treatment at the outset with radiation, TMZ, and Optune™ (TTField) therapy has not been studied and may require adjustments for safety and tolerability.

1. Radiation therapy

Subjects will receive radiation therapy within 4-6 weeks of their surgical resection or 2-4 weeks of their biopsy for the purpose of ensuring proper wound-healing. Treatment will be mapped

and delivered by a qualified radiation oncologist to a target dose of 60 Gray (Gy) in equally divided fractions of 2 Gy to the Clinical Target Volume (CTV) delivered over 30 fractions over a period of 42 days + 7 days (about 6 weeks; to Day 49 + 7 days). At the discretion of the Radiation Oncologist, particularly for large treatment volumes, the prescription dose may be 59.4 Gy in 33 fractions of 1.8 Gy. The subject will undergo treatment mapping and production of a high-quality mask to immobilize the head for treatment. An initial CT image of the subject's head is obtained and fused to the post-surgical MRI of the brain for treatment mapping and used for conebeam CT image alignment before treatment delivery. Due to the presence of the transducer arrays on the scalp, a phantom model will be employed to investigate radiation dosimetry effects and any interference with the making of a high-quality immobilization mask. These exploratory studies will provide guidance on any necessary adjustments for subjects for safe and effective radiation treatment of tumor (See RT). Expected and potential treatment-related acute adverse effects include skin reactions, alopecia, headache, fatigue, seizure, tumor necrosis, memory impairment, and altered cognition.

Radiation therapy without interruptions

Completion of radiotherapy course uninterrupted will be prioritized. Grade 3-4 skin toxicity during RT course will result in at least 1 week break from TTF therapy (with reduced Optune dosing for up to one month as above) with resumption following physician evaluation and clearance.

2. Temozolomide chemotherapy

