Subjects will receive TMZ chemotherapy as part of the trimodal therapy phase concurrently with radiation and TTF therapy. This will be administered orally by the subjects at a dose of 75mg/m² (of their body surface area) daily during radiation therapy (typically for 42 consecutive days including on weekends, up to 49 days is acceptable; to Day 49 + 7 days). Subjects will then discontinue the chemotherapy and have a 4-week break after radiation prior to resuming TMZ adjuvant therapy concurrent with TTF therapy alone. Doses will then be administered for 5 consecutive days out of a 28-day cycle. For the first cycle of adjuvant therapy, subjects will be dosed at 150mg/m²/day for 5 days out of 28 days in the first cycle, and increased if tolerated to 200mg/m²/day and continue that dose until the end of chemotherapy. The standard requirement is for 6 cycles of adjuvant treatment post-radiation but this may be extended per the judgment of the subject's treating clinician to no more than 12 cycles of adjuvant TMZ therapy. Please see package insert for full details. Expected and potential treatment-related acute adverse effects include: Nausea, fatigue, constipation, liver toxicity, myelosuppression resulting in thrombocytopenia, leukopenia (or neutropenia), anemia, or pancytopenia.

Initiation of PJP prophylaxis is recommended but each site will be given discretion to follow their institutional protocols.

Dose modifications during Trimodal therapy phase

ANC $\geq 500/\text{mm}^3$ but $< 1,500/\text{mm}^3$ **or** platelet count $\geq 10,000/\text{mm}^3$ but $< 100,000/\text{mm}^3$ **or** grade 2 nonhematologic toxicity (excludes alopecia, nausea/vomiting): Interrupt therapy

ANC $< 500/\text{mm}^3$ **or** platelet count $< 10,000/\text{mm}^3$ **or** grade 3/4 nonhematologic toxicity (excludes alopecia, nausea/vomiting): Discontinue therapy

Dose modifications during adjuvant therapy phase (concurrent with TTFields therapy only)

ANC $< 1,000/\text{mm}^3$, platelet count $< 50,000/\text{mm}^3$, or grade 3 nonhematologic toxicity (excludes alopecia, nausea/vomiting) during previous cycle: Decrease dose by 1 dose level (by $50 \text{ mg/m}^2/\text{day}$ for 5 days), unless dose has already been lowered to $100 \text{ mg/m}^2/\text{day}$, then discontinue therapy.

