Y: Day 1 of the first 2 cycles of adjuvant therapy will fall within the DLT window with continued skin exams (Cycle 1 Day 1 and Cycle 2 Day 1). The subsequent cycles with post-TMZ maintenance TTField therapy will proceed per the standard of care (minimum of 6 cycles, up to 2 years). For continued participation in the trial, patients must continue to follow up every 2-3 months with a repeat MRI of the brain.
Z: To include PFS and OS.
AA: Monitor adverse events through 8 weeks post-RT/TMZ (through Day 1 of first cycle of Cycle 2).
BB: To be stopped post Day 43 visit on Day 49 (+ 7 days, if clinically appropriate).
CC: To be assessed if MRI completed per SOC since last review/contact.
DD: Time that must have elapsed prior to study enrollment (Day 1): 3-6 weeks (21-42 days) from time of definitive surgery or 2-4 weeks (14-28 days) from the time of biopsy for those who were only able to safely have a biopsy and not full resection.
EE: Use MRI from Day 1 Cycle 1 for assessment.
FF: To be completed monthly, may not be available at each visit.
GG: If indicated, per investigator discretion.
HH: Transducer arrays will need to be removed/replaced to complete.

**Please note, the above notations can be found in the body of the protocol, but are listed here as well with the intent of making the study calendar easier to follow.*

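### Study-day labels for stopping RT and temozolomide, and for the two post-RT visits, do not fit every RT schedule the protocol permits

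*Combined protocol and SAP*

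**What the plan says.** **RT start.** Section 6, Sequence of Starting Trimodal Therapy, note C: "RT should be initiated no more than 14 days after the day 1 visit (by Day 15". The nominal start is about Day 8, where the Day 8 visit lists RT initiation.

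**RT course.** Section 6, Treatment Modalities, Radiation therapy, sets 30 fractions of 2 Gy "over a period of 42 days + 7 days (about 6 weeks; to Day 49 + 7 days". At the radiation oncologist's discretion, mainly for large volumes, "the prescription dose may be 59.4 Gy in 33 fractions of 1.8 Gy". No separate calendar is given for that option. The next paragraph adds: "Completion of radiotherapy course uninterrupted will be prioritized".

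**Stop day.** The Day 43 visit text has "Continuation of RT until Day 49 + 7 days, as clinically appropriate", with a matching line for TMZ. Appendix 3, footnote BB, says the same of both: "To be stopped post Day 43 visit on Day 49 (+ 7 days, if clinically appropriate". The TMZ section gives dosing "daily during radiation therapy (typically for 42 consecutive days including on weekends, up to 49 days is acceptable", after which patients "have a 4-week break after radiation prior to resuming TMZ adjuvant therapy".

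**Later visits.** Cycle 1 Day 1 is Study Day 78 ± 5 and Cycle 2 Day 1 is Study Day 106 ± 5. The Adjuvant therapy phase text describes them as 4 and 8 weeks after trimodal therapy. Section 6, Safety Lead-ins, runs the DLT period to 8 weeks after RT ends. Appendix 3, footnote AA, equates 8 weeks after RT/TMZ with Cycle 2 Day 1 and ends adverse-event monitoring there.

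**The concern.** Two anchors are in use. Course length, TMZ break and DLT window are counted from RT itself; the stop and the follow-up visits carry study days counted from enrolment. The two agree for a 30-fraction course started near Day 8 and drift apart when RT starts late.

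A site giving 33 fractions after a late start cannot satisfy both the prescription and the written stop. The visit labels have a related weakness. If Cycle 2 Day 1 is kept inside its study-day window after a late RT end, and monitoring closes there, follow-up is shorter than the 8 weeks that define the primary safety endpoints. The DLT counts in the stopping rules for the 6- and 15-patient lead-ins use the same window.

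**Working it through.** **Inputs.** From Section 6 and Appendix 3: latest RT start Day 15; 30 or 33 fractions; stop Day 49, at most Day 56; Cycle 1 window Day 73-83; Cycle 2 window Day 101-111; mid-break visit Day 64 ± 7. Assumed: five weekday fractions a week, no missed days, weekday Day 1 visit. The pace is not stated, but it is what 30 fractions in 42 days implies.

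**Reproducing the protocol's days.** A 42-day course from Day 8 ends on 8 + 42 − 1 = Day 49; from Day 15 it ends on 15 + 42 − 1 = Day 56. Then 49 + 28 = 77 and 49 + 56 = 105, each within a day of the stated 78 and 106. The labels fit a 42-day course started on Day 8.

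**Course spans.** By weekday counting, 30 fractions span 40 days (Monday start) or 42 days (other starts). 33 fractions span 45 days (Monday-Wednesday start) or 47 days (Thursday/Friday start). Both lie within 42 + 7 = 49 days.

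**End day** = start day + span − 1. The 33-fraction starts that pass Day 56 are:

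| RT start | End of 33 fractions | Days past 56 |
|---|---|---|
| Day 11, Thu/Fri | 57 | 1 |
| Day 12, Fri | 58 | 2 |
| Day 13, Mon-Wed | 57 | 1 |
| Day 14, Mon-Wed | 58 | 2 |
| Day 14, Thu | 60 | 4 |
| Day 15, Mon-Wed | 59 | 3 |
| Day 15, Thu/Fri | 61 | 5 |

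For RT starts on Day 2-15 there are 50 combinations of weekday Day 1 and weekday RT start. Of these, 2 + 1 + 3 + 3 + 1 + 3 + 2 = 15 pass Day 56 with 33 fractions. With 30 fractions none does: the latest end is 15 + 42 − 1 = 56. These are calendar patterns, not patient proportions.

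**Visit windows, in days after RT end** (window day − RT end day):

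| RT end | Cycle 1 (Day 73-83) | Cycle 2 (Day 101-111) |
|---|---|---|
| Day 49 | 24-34 | 52-62 |
| Day 56 | 17-27 | 45-55 |
| Day 60 | 13-23 | 41-51 |
| Day 61 | 12-22 | 40-50 |

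**Allowing ± 5 days around 4 and 8 weeks.** The acceptable ranges are then 23-33 and 51-61 days after RT. A date meeting both the study-day and the RT-based window exists when 83 − RT end is at least 23 and 111 − RT end is at least 51. Both give RT end no later than Day 60. Only Day 61 fails, at 22 and 50 days: 2 of 50 patterns (Day 15 Thursday/Friday, 33 fractions), by one day.

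**Two-week visit.** Its last day is 64 + 7 = 71, which is 71 − 61 = 10 days after the latest RT end. That lies within 14 ± 7 days, so this visit is not missed.

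**Reach.** RT must fall within 6 weeks of resection or 4 weeks of biopsy. A Day 15 start therefore needs enrolment by 42 − 14 = 28 days after resection, where the enrolment window opens at 21. After biopsy it needs enrolment at 28 − 14 = 14 days, the first day allowed.

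**The case against.** The best defence is that the study days are nominal labels and that the rules that matter are tied to RT. The DLT period runs to 8 weeks after RT, the adjuvant phase begins 4 weeks after RT, and the RT text gives a relative length and gives priority to an uninterrupted course. A sensible site would finish the fractions and time the visits from RT. The problem also needs a discretionary fractionation and a start well after the nominal Day 8. Most of this stands, and it keeps the point small. It does not remove the conflict: the current text has no rule for which anchor prevails, and the same parenthesis in the RT section gives both a relative length and a study-day limit that a late 33-fraction course breaks.

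A reader might infer three stronger things.

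- *Patients would be under-dosed.* Stopping literally on Day 56 after a Day 15 start leaves 30 × 1.8 = 54.0 of 59.4 Gy. The priority on completing RT and the 42 + 7 day length make that an unlikely reading.
- *The 4- and 8-week visits are widely missed.* That follows only if 4 and 8 weeks mean exactly 28 and 56 days. The protocol gives these visits ± 5 days, and with that tolerance a compliant date exists in all but 2 of 50 patterns.
- *Toxicity data will be lost.* The documents do not show this. Early closure requires a site to follow the visit label and footnote AA over the DLT definition.

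The general ± 7 day window does not settle the matter, because it yields wherever another window is stated, and ± 5 is stated here.

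**Conclusion.** This is a minor internal inconsistency, established with high confidence. The study-day stop conflicts with a permitted 33-fraction course from RT starts on Day 13-15 and some on Day 11-12, by 1-5 days. It never conflicts with an uninterrupted 30-fraction course.

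The visit labels allow Cycle 2 Day 1, and so the end of monitoring under footnote AA, as early as 45 days after the permitted Day 56 RT end and no later than 55. After a Day 61 end the range is 40-50 days. The stated DLT window is 8 weeks.

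The stop-day result rests on five fractions a week: at six, 33 fractions from Day 15 would end on Day 52-53 and fit. Holiday and weather delays, which the protocol excuses, are not counted. The documents do not say how many patients will have 33 fractions or start late; the number is unknown and probably small.

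**What to change.** 1. In the Day 43 visit text, the RT and TMZ sections and footnote BB, replace the Day 49 + 7 limit with completion of the prescribed fractions within 42 + 7 days of the actual RT start. TMZ should end with RT, at 49 days at most. Uninterrupted, 33 fractions then fit from every permitted start.
2. Anchor Cycle 1 Day 1 and Cycle 2 Day 1 to the actual RT end, at + 4 and + 8 weeks, ± 5 days. Bring the calendar headings and the Study Period end into line.
3. In footnote AA, run adverse-event and DLT monitoring to at least 56 days after RT ends, even if the Cycle 2 visit is earlier. Re-anchoring alone is not enough, because + 8 weeks − 5 days still allows closure at 51 days.

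The cost is wording only, with no added patients or scheduled visits. A patient seen before day 56 needs adverse events captured for the remaining few days. Some visits move later. At the ceiling, RT from Day 15 for 49 days ends on 15 + 49 − 1 = Day 63, which puts Cycle 1 nominally on Day 91 and Cycle 2 on Day 119, 13 days after the present nominal days.
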